### **8.1.2 Primary analysis of the primary efficacy variables**

The efficacy variables, change from Baseline to Visit 2 (for all continuous efficacy variables not based on Kinesia-360, i.e. UPDRS Part III and Kinesia-ONE scores) will be analyzed utilizing an analysis of covariance (ANCOVA) with Baseline as a covariate, “center” as factor, and “group” as main factor. The 2 groups are the Experimental Group (EG) and the Control Group (CG).

The 2-sided null and alternative hypotheses are:

- Null hypothesis ( $H_0$ ): EG=CG
- Alternative hypothesis ( $H_a$ ): EG $\neq$ CG

EG: Represents the change from Baseline to Visit 2 for subjects in the Experimental Group.

CG: Represents the change from Baseline to Visit 2 for subjects in the Control Group.

The efficacy analysis will be performed on the FAS and observed cases will be utilized. The group effect will be estimated and presented with 95% 2-sided CIs and p-values.

The single items of UPDRS Part III and the sum score will be presented in listings, the sum score will be summarized by group, and the change from Baseline to Visit 2 in UPDRS Part III score will be analyzed using ANCOVA.

The change from Baseline to Visit 2 in each of the Kinesia-ONE scores will be analyzed using ANCOVA.

The Neupro dose per 24h at Visit 2 will be summarized by group, as well as the Neupro starting dose per 24h. Both assessments of Neupro dose will be related in a shift table by group. In addition, Neupro dose and Neupro dose change will be tabulated as continuous variable.

The number of Neupro dose changes after first administration until Visit 2 will be summarized by group.

The comparison of the rate of discontinuation of treatment with Neupro during the course of the study for the control group and the experimental group will be performed using logistic regression with factors for treatment and center.

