
2 INTRODUCTION

Neupro is approved for the treatment of the signs and symptoms of early-stage idiopathic Parkinson's disease as monotherapy (ie, without levodopa) or in combination with levodopa, ie, over the course of the disease, through to late stages when the effect of levodopa wears off or becomes inconsistent and fluctuations of the therapeutic effect occur (end of dose or "on-off" fluctuations).

Dosing in patients with early-stage Parkinson's disease consists of a single daily dose initiated at rotigotine 2mg/24h and then increased in weekly increments of rotigotine 2mg/24h to an effective dose up to a maximum dose of rotigotine 6mg/24h. Rotigotine 4mg/24h may be an effective dose in some patients. For most patients an effective dose is reached within 3 or 4 weeks at doses of rotigotine 6mg/24h. The maximum approved dose is rotigotine 6mg/24h (NEUPRO [package insert]. 2016 [[Section 15](#)]).

Dosing in patients with advanced-stage Parkinson's disease with fluctuations consists of a single daily dose that should be initiated at rotigotine 4mg/24h and then increased in weekly increments of rotigotine 2mg/24h to an effective dose up to a maximum dose of rotigotine 8mg/24h. Rotigotine 4mg/24h or rotigotine 6mg/24h may be effective doses in some patients. For most patients with advanced-stage Parkinson's disease, an effective dose is reached within 3 to 7 weeks at doses of rotigotine 8mg/24h. The maximum approved dose is rotigotine 8mg/24h (NEUPRO [package insert]. 2016 [[Section 15](#)]).

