3 STUDY OBJECTIVES

3.1 Primary objectives

The primary objectives of this study are to:

- Evaluate whether Parkinson's disease motor symptoms in subjects starting Neupro can be improved by using feedback of motor symptom data from the Kinesia-360 wearable technology presented to subjects and Investigators in addition to standard clinical practice as compared with only standard clinical practice.
- Evaluate the Neupro dosing regimen when using feedback of motor symptom data collected with the Kinesia-360 wearable technology in addition to standard clinical practice as compared with only standard clinical practice.
- Evaluate whether subjects with Parkinson's disease are more likely to continue the usage of Neupro if Parkinson's disease motor symptom data collected using the Kinesia-360 wearable technology is used to provide the subjects with feedback on the status of their Parkinson's disease motor symptoms and is used in addition to standard of care for titrating their Neupro dosing regimen.

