5 STUDY DESIGN

5.1 Study description

PD0049 is a multicenter, open-label, two-arm, 12-week study in subjects with Parkinson's disease. On Day 1, eligible subjects will be randomized to either the Control Group or the Experimental Group in a 1:1 fashion. In both groups, subjects will use the Kinesia-ONE wearable device in-clinic at Visit 1 and Visit 2 for recording of specific motor symptoms, and subjects randomized to the Experimental Group will also use the Kinesia-360 wearable device at home while awake for continuous measurement of motor symptoms. The Investigator will use these symptom data to provide feedback to subjects on their motor symptoms and to supplement standard of care to titrate the optimal dose of Neupro for any given subject. In the Control Group, subjects will not use any wearable device at home, and the Investigator will use only standard of care to titrate the optimal Neupro dose.

Subjects in the Control Group and the Experimental Group will start treatment with Neupro 2mg/24h or 4mg/24h (at the Investigator's discretion and according to the disease stage of the subject) preferably on Day 1 (but no later than Day 4) or Day 4, respectively. Evaluations conclude 12 weeks after the start of treatment with Neupro (ie, at Visit 2).

The decision to prescribe Neupro must be made by the Investigator independent of his/her decision to include the subject in the study. The subject's treatment/Neupro intake must be within the terms of the marketing authorization; Neupro will not be supplied by UCB.

A schedule of study assessments is presented in [Table 5-1](#); for a detailed rationale of the study design see [Section 5.3](#).

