5.1.2 Planned number of subjects and sites

This study will be conducted in approximately 6 sites and will include a total of approximately 40 subjects (20 subjects in the Experimental Group and 20 subjects in the Control Group). Of note, a single site will not randomize more than 20 subjects.

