## **2.2 Study variables**

### **2.2.1 Efficacy variables**

#### **2.2.1.1 Primary efficacy variables**

The primary efficacy variables of this study are:

- Change from Baseline (Visit 1/Week 1) to Visit 2 (Week 12/3 months after start of treatment with Neupro) in Unified Parkinson's Disease Rating Scale (UPDRS) Part III Motor Score
- Change from Baseline (Visit 1/Week 1) to Visit 2 (Week 12) in Kinesia-ONE variables:
  - finger tapping speed score
  - rest tremor score
  - averaged finger tapping speed and resting tremor scores
  - postural tremor score
  - finger tapping amplitude score
  - hand grasp speed score

- hand grasp amplitude score
- rapid alternating movement speed score
- rapid alternating amplitude score
- dyskinesia score
- kinetic tremor score
- rapid alternating movement rhythm score
- hand movements rhythm score
- finger tapping rhythm score
- average Kinesia-ONE score
- Neupro dose per 24h at Visit 2 (Week 12)
- Number of Neupro dose changes during the study (between Visit 1 and Visit 2)
- Discontinuation of treatment with Neupro during the course of the study

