### **8.2.4 Unified Parkinson's Disease Rating Scale Parts I, II, IV**

The UPDRS Part I (Mentation, Behavior, and Mood) includes intellectual impairment, thought disorder, depression, and motivation/initiative (4 questions=16 points maximum).

The UPDRS Part II (Activities in Daily Living) consists of 13 items scored between 0 and 4. It includes speech, salivation, swallowing, handwriting, cutting food and handling utensils, dressing, hygiene, turning in bed and adjusting clothes, falling (unrelated to freezing), freezing when walking, walking, tremor, and sensory complaints related to Parkinsonism (13

questions=52 points maximum). The sum score will be calculated as the sum of the 13 individual scores. If one or more items are missing, the sum score will also be missing.

The UPDRS Part IV (Complications of Therapy) consists of 11 questions. It includes dyskinesias, duration, disability, painful dyskinesias, early morning dystonia, clinical fluctuations, presence of anorexia, nausea or vomiting, sleep disturbance, and symptomatic orthostasis (11 questions).

The single items of UPDRS Parts I, II, and IV, and the sum scores will be presented in listings. The UPDRS Part IV will be presented separately for each item, the sum scores of UPDRS Part I and II will be summarized by group, and the change from Baseline to Visit 2 in UPDRS Part II score will be analyzed using ANCOVA as described in [Section 8.1.2](#).

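### Visit 2 Neupro dose, a primary variable, gets no between-group estimate and no adjustment for pre-randomisation disease stage, although the protocol ties dose to stage

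*SAP*

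**What the plan says.** Visit 2 dose is listed among the primary efficacy variables (Protocol 4.1.1, SAP 2.2.1.1). It serves the second primary objective: "Evaluate the Neupro dosing regimen when using feedback of motor symptom data collected with the Kinesia-360 wearable technology", compared with standard practice alone (Protocol 3.1).

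For this variable SAP 8.1.2 states: "The Neupro dose per 24h at Visit 2 will be summarized by group, as well as the Neupro starting dose per 24h". The same paragraph adds a shift table from starting to Visit 2 dose by group, and a continuous tabulation of dose and dose change. The ANCOVA there is confined to UPDRS Part III and the Kinesia-ONE scores, and discontinuation gets a logistic regression with treatment and center. SAP 8.1 speaks more broadly of ANCOVA for change in the primary variables, but 8.1.2 does not carry it to dose, which has no pre-treatment value.

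Protocol section 2 describes titration in early-stage disease from 2 mg/24h to "an effective dose up to a maximum dose of rotigotine 6mg/24h", and in advanced-stage disease with fluctuations from 4 mg/24h to "an effective dose up to a maximum dose of rotigotine 8mg/24h". Subjects of any stage may enrol (Protocol 1). Randomisation is stratified by site only (Protocol 7.5). Adjustment elsewhere is for baseline value and center (SAP 4.1), and no subgroups are defined (SAP 4.8). SAP 6.2 takes starting dose as the indicator of stage.

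**The concern.** The dosing objective is comparative, but the plan gives it only side-by-side summaries. Stage should account for part of the spread in Visit 2 dose, because the protocol itself gives the two stages different ranges. With about 20 subjects per group and no stratification by stage, the groups can differ by several advanced-stage subjects by chance, and the raw dose difference moves with them. SAP 4.1 justifies its adjustments by the likely influence of baseline and center on outcome. The same reasoning applies to stage for dose, where no baseline value of the variable exists to do the work.

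The planned shift table and dose change refer to starting dose. That dose is first given after open-label randomisation, and neither display yields an adjusted group difference.

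**Working it through.** There is no plan figure to reproduce: Protocol 12.8 and SAP 2.4 give about 40 subjects without a formal calculation.

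**Inputs from the documents.** n = 20 per group (Protocol 5.1.2); about 6 sites; starting doses 2 and 4 mg/24h and maxima 6 and 8 mg/24h (Protocol 2).

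**Assumptions, because the documents give none.** Advanced-stage share p = 0.5 (range 0.2 to 0.7). Difference in mean Visit 2 dose between stages d = 1 to 2 mg/24h, where 2 is the difference between the two maxima (8 − 6). Within-stage SD s = 1.0 to 2.0 mg/24h. Stage known without error.

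**Formulas for the group difference.**
- Unadjusted SE = √[2(s² + d²p(1−p))/n]
- Stage-adjusted SE = s√(2/n)

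For d = 2 and s = 1.5: √[2(2.25 + 1)/20] = √0.325 = 0.570, against 1.5 × √0.1 = 0.474. The ratio is 1.20.

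| d | s | SE unadjusted | SE adjusted | Ratio |
|---|---|---|---|---|
| 1 | 1.0 | 0.354 | 0.316 | 1.12 |
| 1 | 1.5 | 0.500 | 0.474 | 1.05 |
| 1 | 2.0 | 0.652 | 0.632 | 1.03 |
| 2 | 1.0 | 0.447 | 0.316 | 1.41 |
| 2 | 1.5 | 0.570 | 0.474 | 1.20 |
| 2 | 2.0 | 0.707 | 0.632 | 1.12 |

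Over p = 0.2 to 0.7 the excess runs from 2 to 12% at d = 1 and from 8 to 41% at d = 2. A simulation of 20,000 trials per setting at p = 0.5 and d = 2, which includes the cost of estimating the stage term, gives ratios of 1.40, 1.19 and 1.11.

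**The same effect seen as imbalance.** The SD of the difference in advanced-stage share is √(2 × 0.25/20) = 0.158. Multiplying by 1.96 × d gives a 95% range of ±0.31 mg/24h (d = 1) to ±0.62 mg/24h (d = 2). Treating the groups as independent binomials and ignoring site blocks, an imbalance of at least 4 subjects has probability 0.27. At exactly 4 of 20 and d = 2 the raw difference shifts by 0.20 × 2 = 0.40 mg/24h. In simulation the adjusted difference shifts by about zero.

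This is not a second loss. For d = 2 and s = 1.5 the two variances differ by 0.325 − 0.225 = 0.100, which is (2 × 0.158)².

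**Imperfect stage indicator.** Suppose the indicator captures only half of the between-stage variance (an illustration). For d = 2 and s = 1.5 the residual variance is 2.25 + 0.5 = 2.75, and the ratio is √(3.25/2.75) = 1.09 instead of 1.20.

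**Degrees of freedom.** 40 − 1 − 1 (group) − 5 (six centers) = 33 residual; two more terms leave 31.

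**The case against.** The strongest reply is that no inference on dose is planned. SAP 8.1.2 specifies no model, SE, CI or p-value for it, the trial is a pilot meant to give an impression, and all tests are exploratory (Protocol 12.2, SAP 4.5). A reader might infer that a planned interval is too wide; none exists. That stands, and it locates the gap: the missing item is an estimate, and its covariates come next.

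A reader might also infer that the raw comparison is biased. It is not. The imbalance averages zero over randomisations, and an ordinary unadjusted SE would already include it.

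Second, stage is partly visible already, since starting dose is tabulated and cross-classified with Visit 2 dose by group. A marked imbalance would probably show there. But these displays give no adjusted difference.

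Third, it is tempting to say that starting dose is contaminated by allocation. The documents do not establish this. Subjects are newly prescribed Neupro at entry (Protocol 6.1), the prescribing decision is independent of inclusion (Protocol 5.1), and nothing says when the starting dose was fixed. Nor is the risk excluded: the dose is at the Investigator's discretion, and Experimental Group subjects start on Day 4, after wearing Kinesia-360 on Days 2 and 3. This supports caution about starting dose as the main covariate, not a ban on using it.

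Fourth, stage proxies are imperfect. Levodopa use does not define advanced disease, since Protocol section 2 describes combination with levodopa over the whole course. A stage factor without a written rule would add analyst choice to a SAP already amended after the Data Evaluation Meeting. Both points stand and shape the fix.

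**Conclusion.** The point holds as a gap in estimation and an avoidable loss of precision. A primary variable serving a comparative objective has no between-group estimate, and Visit 1 information on stage and severity goes unused for it.

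With half the subjects advanced-stage, 20 per group, error-free stage and a within-stage SD of 1.0 to 2.0 mg/24h, leaving stage out makes the SE 3 to 12% larger at a 1 mg/24h stage gap and 12 to 41% larger at 2 mg/24h. All these inputs except the group size are assumptions, and a realistic indicator would recover only part of the gain. At the smaller gap the benefit is minor; near the larger one it is material for a trial of this size. The documents support neither systematic bias nor an effect of allocation on starting dose. For an exploratory pilot this is a cheap improvement, not a flaw that invalidates the plan.

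**What to change.** In SAP 8.1.2, add a linear model for Visit 2 dose with group, center and two covariates recorded at Visit 1 before randomisation:
- baseline UPDRS Part III;
- one binary indicator with its rule written out, for example any clinical fluctuation recorded in UPDRS Part IV. SAP 8.2.4 says of Part IV: "It includes dyskinesias, duration, disability, painful dyskinesias, early morning dystonia, clinical fluctuations".

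Protocol 8.1 lists the UPDRS ahead of randomisation on Day 1; the SAP should state that only pre-randomisation values are used. Report the adjusted group difference with its 95% CI beside the planned raw summaries, labelled exploratory.

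State a simple rule that keeps subjects with a missing covariate, such as overall-mean imputation of that covariate. Otherwise subjects could be lost: one missing item makes the Part III sum missing (SAP 8.1.1.1), while Neupro dose alone can qualify a subject for the FAS (SAP 3.5.3).

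Do not make starting dose the main covariate. A model adjusted for it may be shown as a sensitivity analysis.

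The cost is a short SAP edit, one model on data already collected, and about two of 33 residual degrees of freedom.

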7.5 Randomization and numbering of subjects

Subjects will be randomized (1:1) to either the Control Group (without Kinesia-360 device to measure motor symptoms at home) or the Experimental Group (with Kinesia-360 device to measure motor symptoms at home) during the Screening Visit (Visit 1). The randomization will be stratified by site. A randomization list for each site with a block size of 4 will be provided to

the site. Each subject will receive a 5-digit number assigned at Screening that serves as the subject identifier throughout the study.

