### 2.1 Study objectives

#### 2.1.1 Primary objectives

The primary objectives of this study are to:

- Evaluate whether Parkinson's disease motor symptoms in subjects starting Neupro can be improved by using feedback of motor symptom data from the Kinesia-360 wearable technology presented to subjects and Investigators in addition to standard clinical practice as compared with only standard clinical practice.
- Evaluate the Neupro dosing regimen when using feedback of motor symptom data collected with the Kinesia-360 wearable technology in addition to standard clinical practice as compared with only standard clinical practice.
- Evaluate whether subjects with Parkinson's disease are more likely to continue the usage of Neupro if Parkinson's disease motor symptom data collected using the Kinesia-360 wearable technology is used to provide the subjects with feedback on the status of their Parkinson's disease motor symptoms and is used in addition to standard of care for titrating their Neupro dosing regimen.

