## 2.4 Determination of sample size

Due to the character of the study, no formal sample size estimation can be performed. A sample size of approximately 40 will be regarded to be sufficient to get an impression of the effect of the device on the efficacy variables.

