#### **3.7 Center pooling strategy**

No pooling of centers is planned for this study.

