## **4.4 Multicenter studies**

No multicenter analyses are planned. Therefore, this section is not applicable for this study.

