## **4.5 Multiple comparisons/multiplicity**

All statistical tests are considered exploratory, and calculated p-values  $<0.05$  do not indicate statistical significance, since no alpha adjustment will be performed.

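### Neupro discontinuation is tested by logistic regression in about 40 subjects with no sparse-data method named, so with few events the treatment odds ratio may have no finite estimate

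*SAP*

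**What the plan says.** - **Objective.** The third primary objective asks whether subjects given Kinesia-360 feedback "are more likely to continue the usage of Neupro" (SAP 2.1.1). Treatment discontinuation is listed as a primary efficacy variable in SAP 2.2.1.1.
- **Model.** SAP 8.1.2 says the comparison of discontinuation rates "will be performed using logistic regression with factors for treatment and center". No estimation method is given. The same section promises the group effect with 95% confidence intervals and p-values.
- **Centers.** SAP 3.7: "No pooling of centers is planned for this study". SAP 4.4: "No multicenter analyses are planned. Therefore, this section is not applicable for this study".
- **Size.** About 40 subjects, 20 per group, at about 6 sites (SAP 2.3), and "no formal sample size estimation can be performed" (SAP 2.4). Protocol 5.1.2 adds that "a single site will not randomize more than 20 subjects".
- **Allocation.** 1:1, stratified by site: "A randomization list for each site with a block size of 4" (Protocol 7.5).
- **Status of the tests.** "All statistical tests are considered exploratory" (SAP 4.5).
- **Not covered.** SAP 4.2 (missing data) and SAP 8.1.4 (sensitivity analyses) say nothing about exact or penalised estimation, dropping center, or a model that does not converge.

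**The concern.** Treatment plus about six center levels is a large model for 40 subjects when the outcome may occur only a handful of times. Two different things can go wrong under ordinary maximum likelihood:

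1. A center with no discontinuations gets an infinite coefficient and adds nothing to the treatment comparison. The treatment odds ratio usually stays finite.
2. The treatment odds ratio itself has no finite estimate, mainly because one group has no discontinuations. Its Wald interval and p-value are then unusable.

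The second is the one that matters. It would remove the only planned between-group estimate for a primary objective, and a replacement would have to be chosen in an open-label study with the group results known.

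**Working it through.** The plan states no power, event count or discontinuation rate, so there is no figure to reproduce. All rates below are assumptions.

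**When the estimate fails.** In center c, let x of m Control subjects and y of n Experimental subjects discontinue. In a model with center and group, the group coefficient has no finite maximum-likelihood estimate if and only if

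- every center has x = 0 or y = n, or
- every center has y = 0 or x = m.

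The main route is a whole group with no events.

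**Closed form for a zero-event group, 20 per group.** With a common rate p,

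P = 2(1−p)^20 − (1−p)^40.

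At p = 0.10 this is 2(0.1216) − 0.0148 = 0.228. For 30% vs 12.5%, 0.70^20 + 0.875^20 minus their product is 0.0008 + 0.0692 − 0.0001 = 0.070.

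**Simulation of the planned model.** 4,000 trials per cell; 40 subjects at 6 sites of (20,4,4,4,4,4), (7,7,7,7,6,6) or (12,8,8,4,4,4); site-stratified blocks of 4. Ranges are over the three layouts. The last column counts trials with at least one center that adds no information on treatment, in the main because it has no events.

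| Assumed rate, Control / Experimental | Zero-event group (closed form) | Treatment odds ratio not finite | At least one uninformative center |
|---|---|---|---|
| 10% / 10% | 22.8% | 22–24% | 98–100% |
| 15% / 15% | 7.6% | about 8% | 92–98% |
| 20% / 20% | 2.3% | about 3% | 78–93% |
| 30% / 30% | 0.2% | 0.3% or less | 44–77% |
| 30% / 12.5% | 7.0% | about 8% | – |

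**Exact enumeration.** For sites of 8,8,6,6,6,6 split evenly, the treatment odds ratio is not finite with probability 58.9% at 5%/5%, 43.7% at 10%/5%, 22.9% at 10%/10% and 13.3% at 20%/10%. With no center factor, the 10%/5% and 20%/10% figures are 43.6% and 13.2%. Over all cases run, center adds about 0 to 0.7 percentage points.

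**One data set.** Take 4/20 Control discontinuations in four different centers and 0/20 Experimental. Ordinary maximum likelihood reaches a log odds ratio of −9.8 (SE 34.5) after 10 iterations and −24.8 (SE about 62,000) after 25. Firth's method with the same factors gives −2.16 (odds ratio 0.115, SE 1.25).

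**Operating characteristics.** Two-sided 5% test, same 4,000-trial simulation, with a non-finite Wald result counted as no rejection. The 30% vs 12.5% case has odds ratio (0.125/0.875)/(0.30/0.70) = 1/3.

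| | Default Wald | Firth, penalised likelihood ratio |
|---|---|---|
| Type I error at 10% | 0.3–0.5% | 1.9–2.6% |
| Type I error at 20% | about 3% | 4.4–4.8% |
| Type I error at 30% | 5.5–5.7% | 4.7–5.2% |
| Power, 30% vs 12.5% | 18–19% | 25–27% |

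Firth gave a finite odds ratio in every trial. A smaller run (1,000 trials per cell, two layouts) put power at 16% and 22–23%. Fisher's exact test with 20 per group has size 1.2% at a 10% rate, so part of the conservatism comes from sparse data and not from the model.

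**The case against.** **Center is not the main cause.** A model without center would fail almost as often, and pooling alone would not cure it. This stands. Event-free centers are common but leave the treatment odds ratio finite in most cases, so the figures that count are those for the treatment odds ratio.

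**The size rests on an assumed rate.** This also stands. At 20–30% in both groups, failure is rare and Wald type I error is roughly 3–5.7%. The mechanism is certain; its practical weight is not.

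**The tests are exploratory and other outputs exist.** The SAP also plans a Neupro discontinuation listing, a disposition summary and a table of adverse events leading to discontinuation. Information on discontinuation would not be lost, but none of these outputs is the promised between-group estimate with an interval. In a pilot, that estimate is what the analysis is for.

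**The timing is already late.** The SAP was amended after the Data Evaluation Meeting, so a further change would not clearly precede data review. That is fair, but a method fixed before the model is fitted is still better than one chosen after it fails.

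**The remedy is partly a preference.** Exact conditional logistic regression or a stratified exact test would also deal with sparse data, and neither was compared here. The Newcombe interval ignores site stratification. The power gain depends on the penalised likelihood-ratio test: in a 1,500-trial check, Firth with a Wald test had only 18.5–18.7% power, and an ordinary likelihood-ratio test over-rejected at 7–10%.

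**The analysis set is unclear.** SAP 8.1.2 uses the FAS, which needs Visit 2 values, while SAP 10.4.2 also calls discontinuation a safety variable. Subjects who stop Neupro without a withdrawal visit could be left out under any model. This is a separate question and does not weaken the point.

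**Conclusion.** The concern holds. The SAP names no way to estimate or test the discontinuation effect when events are sparse, and this is the only between-group test for the third primary objective. With about 4 events expected in total (10% of 40), the planned odds ratio has no finite estimate in roughly one trial in four or five. With 8 expected (20%), this falls to about 3%, and with 12 (30%) it is negligible. A real reduction in one group raises the risk: about 8% at 30% vs 12.5%, and 44% at 10% vs 5%. These figures assume 40 analysed subjects, six sites and the stated rates, none of which is fixed by the documents beyond approximate numbers of subjects and sites. Because the tests are exploratory, the SAP should be changed, but the gap does not threaten the trial's conclusions.

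**What to change.** In SAP 8.1.2, specify Firth-penalised logistic regression with treatment and center, with a profile penalised-likelihood 95% CI and p-value. Report beside it the risk difference with a Newcombe 95% CI. By full enumeration at 20 per group, that interval has coverage of 95–98% at the assumed rates and an average half-width of 21–26 percentage points.

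The cost is one or two sentences. Firth estimation is an option in the SAS logistic procedure, the planned factors stay, and no new data are needed. The drawback is slight shrinkage towards no effect: at a true log odds ratio of −1.10, the mean Firth estimate was −1.07 to −1.09. The gain in power is modest, power stays low, and the test remains exploratory.
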